## **7.5      Baseline Definition**

The baseline is the results measured at Visit 3 prior to dosing or Visit 2 if Visit 3 is not available.

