Pharmacokinetics: Plasma LY3451838 PK (e.g., C_{max} , $AUC_{0-\infty}$) will be calculated using noncompartmental methods. Pharmacokinetic parameters will be summarized by dose level using descriptive statistics. Dose proportionality will be assessed. Mean and individual LY3451838 plasma concentration-time curves will be presented. Absolute bioavailability will be calculated based on data from the IV and SC cohorts.

2 Schedule of Activities

Study Schedule Protocol JAH-MC-LAJA – Part A (Intravenous Administration) and Part B (Subcutaneous Administration)

| Study Visit | 1 | 2 | 3 | 4 | 5 | 6 | 7 | 8 | 9 | 10 | 11 | 12 | 13 | 14 | 15 | 16 ^a |
|---|-----|----------------|---------------------------------------|---------------------------------------|-----------------|---|---|--------------------|------------|------------|------------|------------|------------|------------|------------|---------------------|
| Study Day | -28 | -1 | 1 | 2 | 3 | 5 | 7 | 9 (-1 to +2) | 15 (±2) | 22 (±3) | 29 (±3) | 43 (±3) | 57 (±4) | 71 (±4) | 85 (±7) | 141 / ED (±7) |
| Visit Type | S | A | I | I | D | O | O | O | O | O | O | O | O | O | O | O |
| Informed consent | X | | | | | | | | | | | | | | | |
| Medical history | X | | | | | | | | | | | | | | | |
| Height/weight ^b | X | | X | | | | | | | | X | | X | | X | X |
| Medical Assessment ^c | X | X ^d | X | X | X | X | X | X | X | X | X | X | X | X | X | X |
| Neurological examination | X | X ^d | | X | | X | | | | X | | X | | | | X |
| Electrocardiogram ^e | X | X ^d | Predose, 1, 3 h | 24 h (± 90 m) | X | X | X | X | X | X | | X | | X | | X |
| Vital signs ^{f, g} | X | X ^d | Predose, EOI ^h , 1, 3 h | 24 h (± 90 m) | X | X | X | X | X | X | X | X | X | X | X | X |
| Orthostatic BP and pulse rate | | | Predose, 1 h | 24 h | | | X | | X | | X | | | | | X |
| Pregnancy test (urine) | X | X ^d | | | | | | | | | X | | X | | | X |
| Screening tests | X | | | | | | | | | | | | | | | |
| Eligibility review | | X ^d | | | | | | | | | | | | | | |
| Study drug administration | | | X | | | | | | | | | | | | | |
| Hematology and chemistry ⁱ | | X ^d | Predose | X | X | X | X | X | X | X | X | X | X | X | X | X |
| C3, C4, CRP and ESR | X | | Predose | X | | X | | X | | X | | X | | | | |
| Urine analysis | | X ^d | | X | | X | | X | | X | | | | | | |
| PK sample ⁱ | | | EOI ^h , 3, 6, 8, 12 h | 24 h (± 60 m), 36 h (± 60 m) | 48 h (±60 m) | X | X | X | X | X | X | X | X | X | X | X |

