Appendix 5. Blood Sampling Summary

This table summarizes the approximate number of venipunctures and blood volumes for all blood sampling (screening, safety laboratories, and bioanalytical assays) during the study.

Protocol J1H-MC-LAJA Sampling Summary – Part A and B

| Purpose | Blood Volume per Sample (mL) | Number of Blood Samples | Total Volume (mL) |
|--|------------------------------|-------------------------|-------------------|
| Screening tests ^a | 21 | 1 | 21 |
| Hematology and chemistry - laboratory tests (fasting) ^a | 10 | 2 | 20 |
| Hematology and chemistry - laboratory tests (non-fasting) ^a | 8 | 13 | 104 |
| Pharmacokinetics | 2 | 19 | 38 |
| Blood discard for cannula patency | 0.3 | 8 | 2.4 |
| Pharmacodynamics (PACAP) | 10 | 12 | 120 |
| Immunogenicity | 10 | 7 | 70 |
| Pharmacogenetics | 10 | 1 | 10 |
| Non-pharmacogenetics | 10 | 2 | 20 |
| Infusion/Hypersensitivity reactions ^a | 8.5 | 1 | 8.5 |
| Total | | | 413.9 |
| Total for clinical purposes [rounded up to nearest 10 mL] | | | 420 |

^a CRP, ESR, C3 and C4 will be tested using chemistry and/or hematology samples. Additional samples, including for hypersensitivity analyses, may be drawn if needed for safety purposes.

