## 4.2 Study Diagram and Flow Chart

Study Schedule Protocol JAH-MC-LAJA – Part A (Intravenous Administration) and Part B (Subcutaneous Administration)

Study Visit	1	2	3	4	5	6	7	8	9	10	11	12	13	14	15	16 a
Study Day	-28	-1	1	2	3	5	7	9 (-1 to +2)	15 (±2)	22 (±3)	29 (±3)	43 (±3)	57 (±4)	71 (±4)	85 (±7)	141 / ED (±7)
Visit Type	S	A	I	I	D	O	O	O	O	O	O	O	O	O	O	O
Informed consent	X															
Medical history	X															
Height/weight b	X		X								X		X		X	X
Medical Assessment c	X	X d	X	X	X	X	X	X	X	X	X	X	X	X	X	X
Neurological examination	X	X d		X		X				X						X
Electrocardiogram e	X	X d	Predose, 1, 3 h	24 h (± 90 m)	X	X	X	X	X	X			X		X	X
Vital signs f, g	X	X d	Predose, EOI h , 1, 3 h	24 h (± 90 m)	X	X	X	X	X	X	X	X	X	X	X	X
Orthostatic BP and pulse rate			Predose, 1 h	24 h			X		X		X					X
Pregnancy test (urine)	X	X d									X		X			X
Screening tests	X															
Eligibility review		X d														
Study drug administration			X													
Hematology and chemistry i		X d	Predose	X	X	X	X	X	X	X	X	X	X	X	X	X
C3, C4, CRP and ESR	X		Predose	X		X		X		X						
Urine analysis		X d		X		X		X		X						
PK sample j			EOI h , 3, 6, 8, 12 h	24 h (± 60 m), 36 h (± 60 m)	48 h (±60 m)	X	X	X	X	X	X	X	X	X	X	X
PACAP sample j			Predose, EOI h 6, 12 h	24 h	48 h	X		X		X		X		X		X
Immunogenicity sample			Predose			X		X		X		X		X		X
Samples for infusion and hypersensitivity reactions j			Predose													
Non-genetic biomarker sample			Predose			X										
PGx sample k			Predose													

Study Visit	1	2	3	4	5	6	7	8	9	10	11	12	13	14	15	16 a
Study Day	-28	-1	1	2	3	5	7	9 (-1 to +2)	15 (±2)	22 (±3)	29 (±3)	43 (±3)	57 (±4)	71 (±4)	85 (±7)	141 / ED (±7)
Visit Type	S	A	I	I	D	O	O	O	O	O	O	O	O	O	O	O
Adverse events									← X →							
Concomitant medications									← X →							

Abbreviations: A = CRU admission; BP = blood pressure; CRU = clinical research unit; D = CRU discharge; ED = early discontinuation; EOI = end of infusion; h = hour; I = inpatient stay; m = minute; O = outpatient; C3 = total complement C3; C4 = total complement C4; CRP = C reactive Protein; ESR = erythrocyte sediment rate; PACAP = pituitary adenylate cyclase-activating polypeptide; PGx = pharmacogenomics; S = screening.

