Note: if multiple procedures take place at the same time point, the following order of the procedure should be used: electrocardiogram, vital signs, and venipuncture. Unless otherwise specified, predose samples may be taken at any time prior to dosing, based on CRU activity schedule.

- a in case of early discontinuation/withdrawal, the subject should undergo all Visit 16 activities.
- b Height will be collected at Screening only.
- c Full medical assessment prior to first dose (on Day -1 or Day 1), discharge, and discontinuation visits. Symptom-driven medical assessment as deemed necessary by the Investigator.
- d Day -1 samples/activities could be collected/Performed up to 5 days before the scheduled day of dosing. The medical assessment, neurological examination and eligibility review may be performed pre-dose on Day 1. If screening visit is within 1 week (inclusive) of Day -1, neurological examination, ECG, hematology and chemistry do not need to be repeated.
- e Single electrocardiogram will be collected at Screening and CRU admission only. Triplicate electrocardiograms will be collected at all other timepoints.
- f Vital signs include blood pressure, pulse rate, and body temperature. Single measurements at Screening and CRU admission. Supine triplicate blood pressure and pulse rate at all other timepoints.
- g Body temperature to be obtained as single measurement.
- h End of infusion procedures are only required for Part A of the study – to be performed within 10 minutes from infusion completion.
- i Predose and 24 h (postdose) samples to be collected after at least 8 hours of fasting. PK samples on day 5 and beyond should be obtained at approximately (± 2 hr) the same time of day as the dosing time on day 1.
- j Samples for infusion reactions and hypersensitivity reactions will be collected and stored for all subjects. Post treatment samples (up to 3) will only be collected in subjects who experience moderate to severe infusion reactions or hypersensitivity reactions (as defined in Section 9.4.5.2).
- k If sample not collected as indicated in Study Schedule table, it may be collected a following visit.

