### **7.3 Missing Data**

No imputation will be made for missing values of safety endpoints except some missing data associated with adverse events (AE), which is specified in Section 9.1.

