### 9.3 Laboratory Tests

The test results of clinical chemistry, hematology and urinalysis are to be summarized by visit. Change from baseline to each post-baseline visit will also be provided. When applicable, all the test result in the following list will be presented.

Clinical Chemistry:	Hematology:
Alkaline phosphatase	Erythrocytes count (RBC)
Alanine Aminotransferase	Hematocrit
Aspartate Transaminase	Hemoglobin
Albumin	Mean cell volume
Blood urea	Mean cell hemoglobin
Bicarbonate	Mean cell hemoglobin concentration
Total Bilirubin	Leukocyte count (WBC)
Calcium	Platelets
C-reactive Protein	Basophils
Complement 3	White blood cell count + differential
Complement 4	Erythrocyte sedimentation rate (ESR)
Sodium	
Total cholesterol	Urinalysis:
Chloride	pH
Creatinine	Specific gravity
Glucose	Blood
Potassium	Nitrite
	Bilirubin
	Ketones
	Protein
	Glucose
	Urobilinogen
	Leukocytes
	Microscopy

Additional analysis will be performed to C3, C4, CRP and ESR.

The number and percentage of subjects with significant decrease in C3 and C4 will be summarized at each of the scheduled visits by treatment and by cohort.

The number and percentage of subjects with significant increase in CRP and ESR will be summarized at each of the scheduled visits by treatment and by cohort.

The significant decrease in C3/C4 will be met if the lab result is classified as NORMAL at baseline, and classified as LOW (<LLN) at post-baseline visits, OR the lab result is classified as LOW at baseline(<LLN), and result gets LOWER than baseline at post-

baseline visits. The significant increase in CRP/ESR will be met if the lab result is classified as NORMAL at baseline, and classified as HIGH ( $>\text{ULN}$ ) at post-baseline visits, OR the lab result is classified as HIGH at baseline( $>\text{ULN}$ ), and result gets HIGHER than baseline at post-baseline visits.

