	Cohort 1 25mgIV N=XX	Cohort 2 75mgIV N=XX	Cohort 3 250mgIV N=XX	Cohort 4 500mgIV N=XX	Cohort 5 1000mgIV N=XX	Cohort 6 1500mgIV N=XX	Cohort 7 250mgSC N=XX		
Post-baseline Visit #1	N	xx	xx	xx	xx	xx	xx	xx	xx
	YES	x(xx.x%)	x(xx.x%)	x(xx.x%)	x(xx.x%)	x(xx.x%)	x(xx.x%)	x(xx.x%)	x(xx.x%)
	NO	x(xx.x%)	x(xx.x%)	x(xx.x%)	x(xx.x%)	x(xx.x%)	x(xx.x%)	x(xx.x%)	x(xx.x%)
Post-baseline Visit #2	N	xx	xx	xx	xx	xx	xx	xx	xx
	YES	x(xx.x%)	x(xx.x%)	x(xx.x%)	x(xx.x%)	x(xx.x%)	x(xx.x%)	x(xx.x%)	x(xx.x%)
	NO	x(xx.x%)	x(xx.x%)	x(xx.x%)	x(xx.x%)	x(xx.x%)	x(xx.x%)	x(xx.x%)	x(xx.x%)

...

The baseline is the measurement at Visit 3 prior to dosing, or Visit 2 whichever is the last available one.  
 Program: 14.3.4.4.xxx.sas

Eli Lilly and Company - PROTOCOL: J1H-MC-LAJA  
 A Safety, Tolerability, and Pharmacokinetics Study of LY3451838 in Healthy Subjects

Table 14.3.4.5  $\bar{T}$  Immunogenicity (Safety)

	LY3451838							Total LY	Placebo
	Cohort 1 25mgIV N=XX	Cohort 2 75mgIV N=XX	Cohort 3 250mgIV N=XX	Cohort 4 500mgIV N=XX	Cohort 5 1000mgIV N=XX	Cohort 6 1500mgIV N=XX	Cohort 7 250mgSC N=XX		
Subject Evaluable for TEADA*	x (xx.x%)	x (xx.x%)	x (xx.x%)	x (xx.x%)	x (xx.x%)	x (xx.x%)	x (xx.x%)	x (xx.x%)	x (xx.x%)
Subject with ADA Detected at Baseline	x (xx.x%)	x (xx.x%)	x (xx.x%)	x (xx.x%)	x (xx.x%)	x (xx.x%)	x (xx.x%)	x (xx.x%)	x (xx.x%)
Subject with TEADA+ at Post-baseline**	x (xx.x%)	x (xx.x%)	x (xx.x%)	x (xx.x%)	x (xx.x%)	x (xx.x%)	x (xx.x%)	x (xx.x%)	x (xx.x%)
Treatment-Induced	x (xx.x%)	x (xx.x%)	x (xx.x%)	x (xx.x%)	x (xx.x%)	x (xx.x%)	x (xx.x%)	x (xx.x%)	x (xx.x%)
Treatment-Boosted	x (xx.x%)	x (xx.x%)	x (xx.x%)	x (xx.x%)	x (xx.x%)	x (xx.x%)	x (xx.x%)	x (xx.x%)	x (xx.x%)

\* Subjects evaluable for TEADA if there is at least one baseline assessment and at least post-baseline assessment of ADA.

\*\* Treatment-emergent ADAs are defined as those with a titer 2-fold (1dilution) greater than the minimum required dilution if no ADAs were detected at baseline (treatment-included ADA) or those with a 4-fold (2 dilutions) increase in titer compared to baseline if ADAs were detected at baseline (treatment-boosted ADA).

Program: 14.3.4.5.xxx.sas

Eli Lilly and Company - PROTOCOL: J1H-MC-LAJA  
 A Safety, Tolerability, and Pharmacokinetics Study of LY3451838 in Healthy Subjects

Table 14.3.4.6  $\bar{T}$  PACAP Concentration (Safety)

3451838P		LY3451838							Total LY	Placebo

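### For C3, C4, CRP and ESR, the SAP's fallback baseline is Visit 2, where the current schedule has no such test, and the scheduled screening value is not allowed

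*SAP*

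**What the plan says.** SAP 7.5 (Baseline Definition) gives a single rule: "The baseline is the results measured at Visit 3 prior to dosing or Visit 2 if Visit 3 is not available". The shell of Table 14.3.4.4, which reports C3, C4, CRP and ESR, restates it: "The baseline is the measurement at Visit 3 prior to dosing, or Visit 2 whichever is the last available one". Neither text mentions Visit 1.

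The protocol's Schedule of Activities (Section 2) gives these four tests a row of their own. It is marked at screening, blank at Visit 2, marked predose at Visit 3, and then continues after dosing: "C3, C4, CRP and ESR | X | | Predose | X". The schedule in SAP 4.2 has the same pre-dose entries.

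SAP 9.3 summarises change from baseline for the laboratory panels. It also defines a significant decrease (C3, C4) or increase (CRP, ESR) from the subject's baseline class together with the post-baseline class or value. SAP 7.3 offers no repair when the baseline is absent: "No imputation will be made for missing values of safety endpoints", apart from some adverse event data. SAP 2 says that the SAP prevails over the protocol where they disagree.

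**The concern.** A fallback is useful only if the fallback visit normally yields a result. For hematology, chemistry and urinalysis it does, because both schedules mark those panels at Visit 2. For C3, C4, CRP and ESR the Visit 2 cell is empty, and the one other scheduled pre-dose result, at screening, is not accepted.

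A subject whose Visit 3 predose result is missing would then have no baseline class, no significant-change flag and no change from baseline at any later visit.

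Protocol 9.4.5.2 names these four tests among those used to look for vasculitis, serum sickness and other type 3 hypersensitivity. Protocol 3.3 reports vasculitis as the dose-limiting toxicity in monkeys. The SAP gives the four tests a dedicated table for this purpose, and with six active subjects per cohort the loss of one is noticeable.

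**Working it through.** The plan states no figure to reproduce here. The check compares the visits at which the tests are scheduled with the visits that the SAP accepts as baseline.

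**Step 1: match the visits.** Each schedule row was split into its 16 visit columns.

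| Source | Pre-dose visits for C3, C4, CRP, ESR | Post-dose visits |
|---|---|---|
| SAP 4.2 | 1, 3 | 4, 6, 8, 10 |
| Protocol Section 2 | 1, 3 | 4, 6, 8, 10, 12 |

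The extra Visit 12 mark in the protocol row may come from the text extraction and does not affect the point.

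- Scheduled before dosing: {1, 3}.
- Accepted as baseline by SAP 7.5 and the table footnote: {2, 3}.
- Overlap: {3}. With Visit 3 missing, no scheduled result remains.
- Overlap if Visit 1 is added as a last resort: {1, 3}. One scheduled fallback then exists.

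**Step 2: where a Visit 2 result could come from.**

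- The summary of amendment (b) in Protocol Appendix 7 says that these tests were moved from Day -1 to predose on Day 1, and its marked-up schedule shows a Visit 2 entry in the row. Subjects enrolled earlier may have Visit 2 values. This is not certain for C3 and C4, because the summary of amendment (a) in Appendix 6 lists only screening and Visits 4, 7, 9 and 11 for them.
- Protocol Appendix 2 and SAP 9.3 list C3, C4 and CRP under chemistry and ESR under hematology, and both panels are scheduled at Visit 2. Protocol Appendix 5 adds: "CRP, ESR, C3 and C4 will be tested using chemistry and/or hematology samples". A Visit 2 panel may therefore have included them, although their own schedule row does not ask for it.

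**Step 3: size.** Each cohort has 6 active and 2 placebo subjects. SAP 6 reports nobody in Cohort 8, so there are 7 × 6 = 42 active and 7 × 2 = 14 placebo subjects. One subject without a baseline is 1/6 = 16.7% of an active cohort, or 1/14 = 7.1% of pooled placebo. On the SAP schedule that subject loses up to 4 tests × 4 visits = 16 flag results.

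The documents give no rate of missing predose results. Let p be an assumed rate, independent between subjects, with no Visit 2 value available. The expected number of cases is 42p. The chance of at least one is 1 − (1 − p)^42 among all active subjects and 1 − (1 − p)^6 in a given active cohort.

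| p | Expected among 42 | At least one among 42 | At least one in a cohort of 6 |
|---|---|---|---|
| 0.1% | 0.04 | 4% | 0.6% |
| 0.5% | 0.21 | 19% | 3% |
| 1% | 0.42 | 34% | 6% |
| 2% | 0.84 | 57% | 11% |
| 5% | 2.1 | 88% | 26% |

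The result depends almost wholly on p.

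**The case against.** The best defence has three parts.

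**The Visit 2 fallback is not empty for everyone.** One SAP covers all cohorts, including subjects who may have had these tests drawn on Day -1 before amendment (b), and for them Visit 2 is a natural baseline. This stands. A reader might infer that the fallback can never work; the amendment history and the panel definitions do not support that. The gap concerns subjects enrolled under the current schedule without an incidental Visit 2 result.

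**Leaving out screening can be deliberate.** Screening may be 28 days before dosing, or more if enrollment was delayed (Protocol 6 and 6.4), while Visit 2 activities are at most 5 days before dosing. Preferring a recent baseline is sound. It supports ranking screening last; it is a weaker reason for having no baseline when screening is the only value.

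**A missing predose result should be rare.** Subjects are admitted on Day -1 and dosed in the unit, predose samples may be taken at any time before dosing, and other predose draws fall on the same day. This also stands, and is why the assumed range starts at 0.1%.

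A reader might also take footnote d of the schedule ("If screening visit is within 1 week (inclusive) of Day -1, neurological examination, ECG, hematology and chemistry do not need to be repeated") to mean that the protocol itself substitutes the screening value as baseline, in conflict with the SAP. The footnote does not say that. It only waives a repeat at Day -1, says nothing about baseline, and leaves predose sampling at Visit 3 in place.

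**Conclusion.** The point holds and is minor. For C3, C4, CRP and ESR, SAP 7.5 and the footnote of Table 14.3.4.4 fall back to a visit at which the current schedules have no such test, and they do not admit the screening value that is scheduled. This follows from the text and needs no assumption. How often it matters does need one: at an assumed missing rate of 0.1% to 5%, the chance of at least one case among 42 active subjects runs from 4% to 88%. Any Visit 2 values that do exist would lower this.

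A reader might infer that a safety signal would be lost or a dose decision affected. The documents do not support that. The affected subject's values still enter the by-visit summaries in SAP 9.3, adverse events are reported separately, and the table shell has an N row at each visit that can reveal a reduced denominator. The primary endpoints are adverse events and serious adverse events, which do not use this baseline. What is lost is that subject's contribution to the flag and change-from-baseline summaries.

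**What to change.** In SAP 7.5, add a sentence for C3, C4, CRP and ESR: baseline is the last non-missing pre-dose value, taken from Visit 3 predose, otherwise Visit 2, and from screening (Visit 1) only when neither is available. Correct the footnote of Table 14.3.4.4 to match.

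The cost is one sentence, one footnote and minor programming. The order keeps the more recent value wherever one exists, so results change only for subjects who would otherwise have no baseline. The downside is an occasional baseline up to about 28 days old, or older if enrollment was delayed; identifying such subjects in the listing would make this visible. If the data are already locked, SAP 2 provides for recording the change in a change request or note to file and in the study report.

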# **8.      DEMOGRAPHICS AND BASELINE CHARACTERISTICS**

## **8.1      Subject Disposition**

The number and percentage of subjects who were screened, enrolled, and treated will be summarized. The number and percentage of subjects who discontinued will also be summarized for each reason of the discontinuation. The analysis will be done by overall patients as well.

## **8.2      Demographics and Baseline Characteristics**

The demographics and Baseline characteristics: gender, race, age, age in three categories (<65, >=65 and <85, >=85), weight, height, and the body-mass index [BMI] will be summarized using descriptive statistics. The analysis will be done by overall patients as well.

## **8.3      Medical History**

The medical history data will be summarized by System Organ Class and preferred term based on coded data by MedDRA. The count and percentage of medical condition per preferred term and SOC will be provided.

# **9.      ANALYSIS OF SAFETY ENDPOINTS**

## 9.1 Adverse Events

The adverse events will be coded by the Medical Dictionary for Drug Regulatory Activities (MedDRA) version 22.0. The treatment-emergent adverse event (TEAE) is defined as any AE emerging or worsening after start of investigational medicinal product (IMP) administration (including placebo). Summary tables will include number of subjects reporting TEAEs and as percentage of number of subjects for the overall subjects. The number of serious TEAEs will be summarized in the appropriate summary table. Summary tables will also be presented for the frequency of adverse events by the MedDRA system organ class and preferred term. Multiple events in the same system organ class for a subject are only counted once in the statistics of that system organ class. The SOC will be presented alphabetically and preferred term within SOC will be presented in descending order of overall frequency. Summary tables will also be provided for the frequency of adverse events by MedDRA system organ class and preferred term and severity of adverse events, and relationship of adverse events to study drug. In these summaries, the most extreme outcome (highest severity and closest relationship to study drug) will be used for those subjects who experience the same adverse event (per preferred term) on more than one occasion.

The number and percentage of patients with Serious TEAE by SOC and preferred term will be summarized. An individual listing of serious TEAE will also be provided.

The summary tables will be performed by each cohort in LY3451838, overall LY3451838 and all placebo subjects combined.

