3.3 Benefit/Risk Assessment

The nonclinical safety and pharmacology information for LY3451838 adequately supports the transition from preclinical status to a clinical, first-in-human study. The risk evaluation of LY3451838 through its properties, nature of the target, non-clinical data in relevant species, target population and dose projections, suggest it not be considered a high risk molecule.

LY3451838 is a novel monoclonal antibody against PACAP, a neuropeptide that is expressed in both central nervous system and peripheral tissues. While pharmacology of this mechanism has not been directly evaluated in humans, AMG301, a monoclonal antibody against PAC1 receptor, has successfully completed phase 1 clinical testing, and is being evaluated for migraine prevention in an ongoing phase 2 trial. The study of AMG301 in phase 2 suggests that blocking at least part of the PACAP pathway did not lead to significant toxicity in humans. The dose-limiting toxicity of LY3451838 was minimal-to-mild vasculitis in multiple organs in monkeys assessed after 8 weekly IV doses of 250 mg/kg, similar to the presentation of vasculitis due to immune response in toxicology species observed with other monoclonal antibodies ([Kronenberg et al. 2017](#)). Immunohistochemistry studies of tissue samples from the 8-week monkey GLP toxicology study demonstrated that the vasculitis was due to immune complex deposition and complement activation. This type of immune response in a single animal species is considered to translate poorly to human safety (EMEA). For this first in human study, the highest dose is limited to 1500 mg, which is predicted to reach an exposure approximately 15-fold lower than the concentration in which vasculitis was observed in monkeys. In addition, PK data will be reviewed with each dose escalation, and an exposure limit will be implemented in this study so that the predicted mean exposure based on observed PK does not significantly exceed that of the no-observed-adverse-effect-level (NOAEL) exposure observed in monkeys.

Immunogenicity and hypersensitivity reactions, including infusion reactions, acute and delayed (including immune complex disease) hypersensitivity reactions are a potential risk for all monoclonal antibodies, including LY3451838. Hypersensitivity risk mitigation in this study includes the administration of a single dose of LY3451838 IV with subsequent close monitoring.

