7.4.1.1 Stopping Rules

If any of the following occur, dosing at the current level and further dose escalation will be discontinued:

1. A single subject experiences an SAE that is related to LY3451838

- a. If an SAE occurs during the infusion of study drug, irrespective of causality, the study drug is discontinued immediately in that subject. No redosing or completion of dosing is considered for that subject regardless of causality. If the infusion SAE is considered related to LY3451838, then the remaining subjects in that cohort are not dosed.
2. Two or more cumulative subjects develop clinically significant acute infusion AEs considered related to LY3451838 during or within 6 hours of completing the infusion that do not resolve with a reduced infusion rate and/or supportive care.
3. Two or more cumulative subjects develop clinically significant hypersensitivity AEs considered related to LY3451838
4. Two or more cumulative subjects experience similar clinically significant events (CSEs) considered related to LY3451838. A CSE will be defined as a moderate-to-severe AE, abnormal clinical sign, or clinical laboratory finding that may pose a risk to the well-being of the subject.
5. 50% or more subjects at a dose level experience moderate or severe AEs that impair normal activities, but do not meet the CSE criteria, and are considered related to LY3451838.

Two or more subjects experience severe adverse reactions, irrespective of their nature.

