7.4.3.2 Management of Infusion Reactions

There is a risk of infusion reaction with any biological agent; therefore, all subjects should be monitored closely. Symptoms and signs that may occur as part of an infusion reaction include, but are not limited to: fever, chills, nausea, headache, bronchospasm, hypotension, angioedema, throat irritation, rash, pruritus, myalgia, and dizziness. In the event that a significant infusion reaction occurs, the following guidance should be followed:

- The drug product infusion should be slowed (for example, reduce infusion rate by 50% [for example, an infusion rate of 12 mL/hr becomes 6 mL/hr or slower]) or stopped based on severity and in accordance with the investigator's assessment:
 - if slowed, the infusion should be completed at the slower rate, as tolerated
 - if determined by the investigator that the infusion should no longer continue, no further attempts to dose the subject should be made
- Supportive care will be administered as required
- If it is determined the subject should not receive further doses of study drug, the subject should complete adverse event and other follow-up procedures per Section 2 of this protocol.

Storage samples should be collected for possible immune safety laboratory testing (Section 9.4.5.2).

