## Safety – Adverse Events

Number	Title	Population
14.3.1.1	Number of Subjects with Treatment-Emergent Adverse Events	Safety
14.3.1.2	Number of Treatment-Emergent Adverse Events	Safety
14.3.1.3	Number of Subjects with TEAE by MedDRA System Organ Class / Preferred Term	Safety
14.3.1.4	Number of Subjects with Serious TEAE by MedDRA System Organ Class / Preferred Term	Safety
14.3.1.5	Number of Subjects with TEAE by MedDRA System Organ Class / Preferred Term and Severity	Safety
14.3.1.6	Number of Subjects with TEAE by MedDRA System Organ Class / Preferred Term and Relationship to Study Drug	Safety
14.3.2.1	Listing of Serious TEAE	Safety

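### The SAP's adverse-event tables do not assure a per-subject count of infusion or hypersensitivity reactions

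*SAP*

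**What the plan says.** Protocol 3.3 states the risk: "Immunogenicity and hypersensitivity reactions, including infusion reactions, acute and delayed (including immune complex disease) hypersensitivity reactions are a potential risk for all monoclonal antibodies", this one included. Two of the stopping rules in protocol 7.4.1.1 are counts of subjects. Rule 2 applies when "Two or more cumulative subjects develop clinically significant acute infusion AEs considered related to LY3451838 during or within 6 hours of completing the infusion" and the events fail to settle with a slower rate or supportive care. Rule 3 applies when "Two or more cumulative subjects develop clinically significant hypersensitivity AEs considered related to LY3451838".

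Protocol 7.4.3.2 gives an open-ended list of how an infusion reaction may present: "fever, chills, nausea, headache, bronchospasm, hypotension, angioedema, throat irritation, rash, pruritus, myalgia, and dizziness". That is 12 entries. Protocol 7.1 has infusion start and stop times, and any early termination, recorded.

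SAP 9.1 plans overall TEAE counts (Tables 14.3.1.1 and 14.3.1.2) and then: "Summary tables will also be presented for the frequency of adverse events by the MedDRA system organ class and preferred term". It adds: "Summary tables will also be provided for the frequency of adverse events by MedDRA system organ class and preferred term and severity of adverse events". A matching table by relatedness is listed in SAP 12.1 as "Number of Subjects with TEAE by MedDRA System Organ Class / Preferred Term and Relationship to Study Drug". A subject is counted once within an organ class (SAP 9.1) and once within a preferred term (footnote to shell 14.3.1.3).

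No output in SAP section 12 is for infusion reactions, hypersensitivity reactions or infusions ended early. The SAP mentions such reactions only in the visit schedule taken over from the protocol and its footnote j. That footnote points to protocol 9.4.5.2 for a definition, but the section describes assessment and sampling and gives no operational case definition.

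**The concern.** The protocol treats these reactions as something a subject either has or does not have. The SAP counts terms. One reaction can produce several terms, and two reactions need not share any, so the unit of the tables is not the unit of the question.

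Adverse events are the primary endpoint, and each cohort plans only 6 active subjects. A reader of the final report will want to know how many subjects at each dose reacted, against how many on placebo. If reactions are reported symptom by symptom, the organ-class and preferred-term tables leave that number open, and at n = 6 a difference of one subject is 17 percentage points.

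**Working it through.** The plan states no figure to reproduce: there is no hypothesis test, and sample size is described as customary for Phase 1 (protocol 10.1).

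**Inputs**
- 6:2 allocation per cohort (protocol 7.2).
- Cohorts 1 to 7; cohort 8 had no subjects at the data lock mentioned in SAP section 6. Planned totals: 7 × 6 = 42 active and 7 × 2 = 14 placebo. Of these, 6 × 6 = 36 active and 6 × 2 = 12 placebo receive an infusion.
- 12 listed signs (protocol 7.4.3.2).

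**Step 1: what each planned table de-duplicates**
- 14.3.1.1: subjects with any, mild or moderate, severe, serious, unrelated or related AE. One count per subject, across all causes and the whole follow-up.
- 14.3.1.2: events, not subjects.
- 14.3.1.3 to 14.3.1.6: one count per subject within an organ class or preferred term.
- None de-duplicates across the terms of one reaction, and none uses time from infusion.

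**Step 2: what preferred-term rows allow**

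If reaction terms show counts m1, m2, … in a group of n, the number of distinct affected subjects lies between max(m) and min(sum of m, n).

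| Counts in the term rows | Distinct subjects, cohort of 6 | Percent of 6 |
|---|---|---|
| 1, 1 | 1 to 2 | 16.7 to 33.3 |
| 1, 1, 1, 1 | 1 to 4 | 16.7 to 66.7 |
| 1, 1, 1, 1, 1, 1 | 1 to 6 | 16.7 to 100 |
| 2, 1, 1 | 2 to 4 | 33.3 to 66.7 |

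Four single-subject terms in the total LY column give 1/42 to 4/42 (2.4% to 9.5%), or 1/36 to 4/36 (2.8% to 11.1%) among infused subjects. These bounds need no probability model.

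**Step 3: does the related-event row close the gap?**

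Two related reactors in a cohort make that row at least 2 of 6. If the reaction terms are the only related events in the cohort, the row gives the exact number. Otherwise it does not. With two reaction terms at one subject each and a related row of 2, there may be two reactors, or one reactor with both symptoms plus another subject with a different related event weeks later.

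**Step 4: how often would two reactors share no row? (illustration only)**

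Assume each of two reactors reports k of the 12 signs, equally likely and independent between subjects.
- Preferred-term rows: k = 2 gives C(10,2)/C(12,2) = 45/66 = 68%; k = 3 gives C(9,3)/C(12,3) = 84/220 = 38%.
- Organ-class rows: the documents give no coding of the signs, so assume seven classes holding 3, 2, 2, 2, 1, 1 and 1 of them. Counting all pairs of symptom sets gives 1992/4356 = 46% for k = 2 and 7228/48400 = 15% for k = 3.

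The range of 15% to 68% shows how far this depends on the assumptions. The conclusion rests on Step 2, not on these percentages.

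**The case against.** The case against is substantial, and several parts of it stand.

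- **The count may appear anyway.** A reader might infer that the number of affected subjects is never shown. The documents do not support that. If the investigator reports one diagnosis, its preferred-term row gives the count directly. Nothing requires separate symptoms to be reported, but nothing requires a single diagnosis either. The count is therefore not assured, rather than absent.
- **A hand count is possible.** Protocol 10.3.1 says AEs will be listed, and SAP Listing 11 is dropped only if raw-data listings suffice. With 42 + 14 = 56 planned subjects this is practical. A listing is not a summary by arm, however, and without an agreed definition two readers can count differently.
- **The stopping rules do not depend on these tables.** A reader might infer that escalation decisions are put at risk. They are not: the investigator and medical monitor review data during the study (protocol 7.4.1 and 10.3.5). Rule 2 also requires clinical significance, relatedness and failure to settle, which a bare symptom count would not test.
- **Related material is covered.** SAP 9.3 counts subjects with C3, C4, CRP and ESR changes, SAP 10.1 covers TEADA, and premedication, recorded as concomitant therapy, falls under SAP 9.6. These are laboratory markers and medications, not clinical reactions.
- **It is not the only named risk.** Vasculitis and neurological effects are also discussed, and no AE of special interest is defined. The SAP does not contradict the protocol here.

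What the objection leaves untouched is that no planned table is specific to reactions and counts each affected subject once.

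**Conclusion.** The point holds as a gap in final reporting. When reactions are recorded as separate symptoms, the organ-class and preferred-term tables leave the number of distinct reactors open: 1 or 2 of 6 with two single-subject terms, 1 to 4 of 6 with four. The related-event row narrows this only when few other related events occur, and it never identifies reactions as such.

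This rests on the outputs named in SAP 9.1 and section 12, and on at least some reactions being reported by symptom, which the documents neither require nor prevent. SAP section 13 says the shells may not show every aspect of the study, but the table list itself contains no such output. The documents do not support reading this as a fault in the real-time stopping decisions, or as proof that the tables would hide a pattern.

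**What to change.** Add to SAP 9.1 and 12.1 one subject-level table by cohort, total LY and pooled placebo:

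- (a) subjects with an investigator-identified infusion reaction, by worst severity and relatedness;
- (b) subjects with a hypersensitivity AE, by worst severity and relatedness;
- (c) subjects whose infusion was terminated early, from the data recorded under protocol 7.1.

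Use infused subjects as the denominator for (a) and (c), since cohort 7 and its placebo subjects are dosed subcutaneously. Fix the definitions and term list before results are seen by arm. If the data lock mentioned in SAP section 6 has passed, record the addition by the route in SAP section 2 (change request or note-to-file, and the CSR).

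A count of subjects with any sign listed in 7.4.3.2 during or within 6 hours after the infusion should be a supportive row only, and only where onset time was recorded. The documents specify time relative to dosing only for injection site reactions. Slowed infusions are left out because the documents do not show that rate reductions are captured.

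The cost is SAP wording, an agreed term list and one extra table. The downside is that nonspecific symptoms such as headache and nausea will be counted in both arms of the supportive row. No clinical rule changes.
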